Repeated measures/study outcomes are included in a standardized battery of test that will be repeated at baseline, endpoint and follow-up. The battery is expected to take approximately 130 minutes to complete.

Tests administered during screening (e.g., the BDI-II, MoCA, BAI, and HVLT, Memory for Intentions Test, and Modified Fatigue Impact Scale) will not be replicated at baseline, but are included in Table 3 below to indicate it is a repeated measure.

Table 3: Repeated Measures Assessment Tools used in the RCT			
Assessment Name (Abbreviation)	Outcome	Construct measure	Time to complete (min)
NIH-EXAMINER components:	1° (composite score of 7 tests listed below)	Executive function	29 total
Dot counting	2°	Working Memory	7
1-back			5
2-back			5
Flanker	2°	Cognitive Control	5
Set Shifting			5
Letter	2°	Verbal Fluency	1
Category			1
Hopkins Verbal Learning Test-Revised (HVLT)	2°	Memory	10
Symbol Digit Modalities Test (SDMT)	2°	Processing speed	5
The Memory for Intentions Test (MIST)	2°	Prospective memory	15
Monetary-Choice Questionnaire	2°	impulsivity	10
Parkinson's Disease-Cognitive Functional Rating Scale (PD-CFRS)	2°	Real-life function	5
The Activity Measure for Post-Acute Care™ (AM-PAC™) –Applied Cognition questionnaire	2°	Real-life function	10
Timed instrumental activities of daily living (iADL)	2°	Real-life function	15
Beck Depression Inventory-II	2°	Depression	10
Beck Anxiety Inventory	2°	Anxiety	10
Starkstein Apathy Scale	2°	Apathy	5
Montreal Cognitive Assessment	2°	Global Cognition	10
Epworth Sleepiness Scale	2°	Sleepiness	5
Modified Fatigue Impact Scale	2°	Fatigue	5
			Total Time: 144 minutes

Phase 4: Intervention

Participants will be randomized to one of three groups: CCT+PRIIS (n=15), CCT+PRIIS control (n=15) or CCT control +PRIIS control (n=15) and issued a VA iPad to take home and complete the study intervention.

Participants and researchers who are administering and scoring outcome measures will be blinded to group assignment. Effectiveness of blinding will be evaluated by using data collected from mid-point and endpoint questionnaires that assess perception of training intervention⁶⁹. The PI will oversee the RCT and coordinate research procedures and thus will not be blinded to treatment assignments. [name], who will be blinded to group assignments, will coordinate sensitive aspects of the study that require blinding.

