CCT training games are developed by Posit Science Corporation, San Francisco, CA, and are designed to train components of EF specifically affected in PD (Table 5). Participants will be asked to complete, at home, 4 sessions/week for 8 weeks. Each session will take 30min; totaling 16hr of CCT training. No dose effect is established for CCT, thus we looked to the literature^{24,28} and expertise of consultants at Posit Science for guidance on the dose, and determined that 16 hours may be sufficient to detect effects of training on cognition. Progress of the training will not be fixed; training modules will be continuously adaptive, following "staircase" procedures⁷⁰, assuring that success in training on ~75% of exercise trials. While this leads to a

different progression of training across participants, it provides a customized, challenging and internally rewarding training experience that should increase performance motivation and optimize learning⁷¹. CCT active control will include 9 entertaining online games that are played on the same platform as the CCT games (Fig 2). Veterans will be asked to complete, at home, 4 sessions/week for 8wk.

For PRIIS, participants will work with a study team member to determine patient-centered prospective memory tasks. Participants will collaboratively agree on problem areas/areas that they would like to manage better (i.e., remember when to take my medicine) formulated in the form of up to three personal rehabilitation goals using the Bangor Goal-Setting Interview (BGSI)⁷². They will rate their own performance on these goals at initial and follow-up assessments. Participants will be taught to form a 'When X, I will do Y', recite the statement aloud three times, and imaging themselves performing the task during the situation in accordance with the statement for 30 s. In addition to the three patient-centered goals, a common goal for all participants in each group will be completing weekly CCT/CCT active control assignments (e.g., on Monday, Wednesday, and Friday, when I eat lunch, I will complete my cognitive training games).

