3.0 Benefits of participation in the study

Individuals that participate may benefit from CCT. The Aims are designed to examine the impact of CCT with or with *PRIIS* to improve cognitive function as well as ADL. Cognitive training programs has been shown efficacious for PD patients as well as patients with other pathologies including TBI and stroke cholinesterase inhibitor medication²³. The information gained in this project will be utilized for further treatment development for cognitive function in Veterans with PD. These pilot data will be used as preliminary data for a larger-scale Merit grant proposal submitted to the VA RR&D service.

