5.0 Data Analysis

All test administrators will undergo the same training. Data will be cleaned and tested for normality (if normality tests fail, appropriate transformations will be made), and proper missing data imputation techniques will be used. Test for multicollinearity will be made. The 3 treatment groups will be characterized using descriptive statistics for demographic factors, disease-related variables, and medication use. Groups will be examined for comparability according to the descriptive variables using ANCOVA and mixed-effects model with random subject effects. For ANCOVA, type I error rate ($\alpha=0.05$) will be adjusted for multiple comparisons using Bonferroni corrections.

Neuropsychological Data Analytical Approaches. For Aims 2 and 3, data will be analyzed using a two-level longitudinal mixed effects model with random subject effects to incorporate correlation of measurements nested within the same subject. Covariates will include medication dose, anxiety, apathy, and depression level. Parameters will be estimated using measurements from baseline, endpoint, and follow-up. The group by time interaction parameter will be used to examine the difference of the trends between the three groups. Significance of this parameter will indicate that treatment is efficacious in terms of EF over time when adjusted by covariates. To assess immediate effects of CCT, an experiment group contrast will be formed using test score means at baseline and endpoint and a control group contrast will be made with those same types of means. To assess sustainability of CCT effects, contrasts using means of test scores at endpoint and follow-up will be made for each group. Estimates of variance components from mixed-model analysis will be used to calculate test statistics. Data analysis will be performed using SAS 9.3 Proc Mixed. This modeling process will be reported for each outcome of interest in Aims 2 and 3. Potential moderators of the effects of the CCT will be explored through Pearson correlations and regression analyses. Factors include, age, age at PD onset, disease duration, MoCA score, depression, anxiety, apathy, L-dopa equivalent dose, PD-MCI subtype diagnosis,

scores on training perception, prior computer use and cognitive training. Co-morbidities and medications will be considered as confounders.

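### The efficacy rule for executive function is an unsigned three-arm interaction naming no pair of arms, and the contrasts that follow do not fully supply the missing comparison.

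*Combined protocol and SAP*

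**What the plan says.** The design has three arms: "Participants will be randomized to one of three groups: CCT+PRIIS (n=15), CCT+PRIIS control (n=15) or CCT control +PRIIS control (n=15"). CCT is given in two of them, and no arm receives PRIIS without CCT. The primary outcome is the NIH-EXAMINER composite (section 1.0, Table 3), part of a "standardized battery of test that will be repeated at baseline, endpoint and follow-up".

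Section 5.0, under the neuropsychological analysis, specifies a mixed model with random subject effects fitted to all three visits. Its test is described as follows: "The group by time interaction parameter will be used to examine the difference of the trends between the three groups". The decision rule comes next: "Significance of this parameter will indicate that treatment is efficacious in terms of EF over time when adjusted by covariates".

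Two kinds of contrast are added. For the immediate effect, "an experiment group contrast will be formed using test score means at baseline and endpoint and a control group contrast will be made" from the same kinds of means. For durability: "To assess sustainability of CCT effects, contrasts using means of test scores at endpoint and follow-up will be made for each group".

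The section does not say that one arm's change is subtracted from another's, which CCT arm or arms form the experiment group, or which direction counts as benefit. A type I error rate and a multiplicity correction are stated only for the ANCOVA.

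**The concern.** The efficacy sentence is a decision rule, and it needs only significance. With three arms there is also no single interaction parameter: there are (3−1)×(3−1) = 4 with categorical time, or 2 with linear time. A significant result says that the trends differ somewhere. It does not say that CCT beat its control, that PRIIS added anything, or that the difference was favourable.

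A difference confined to CCT+PRIIS may be a genuine treatment effect, but it should not be credited to CCT. The durability contrasts, read arm by arm on a battery given three times, cannot separate retention from practice, or from never having gained.

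Section 3.0 says that the pilot is to supply preliminary data for a larger grant proposal. That proposal needs to know which component moved executive function, in which direction and by how much.

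**Working it through.** **Inputs from the documents.** Three arms of 15; three visits; random-subject mixed model; interaction used as the efficacy test. The documents give no SD, correlation, effect size or power figure, so there is no stated result to reproduce.

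**Assumptions.** SD 1; equal correlation r between visits, with r = 0.6, 0.7, 0.8; complete data; categorical time; two-sided 5%; no covariates. Residual df = 3×14×2 = 84; t critical value 1.989.

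**1. The interaction has no sign.** Take a 0.5 SD effect at both endpoint and follow-up.
- The sum of squared interaction effects is 0.5² × (2/3) × (2/3) = 0.111. It is the same if both CCT arms gain, both lose, or only CCT+PRIIS gains.
- Noncentrality λ = 15 × 0.111/(1−r) = 4.17, 5.56, 8.33.
- Noncentral F(4, 84) gives the power in the second column below.
- The signed CCT contrast is the change in CCT+PRIIS control minus the change in CCT control+PRIIS control. Its SE is √(4(1−r)/15).

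| r | Interaction significant, any of the three situations | SE of signed contrast | Favourable and significant: CCT gains | CCT loses | Add-on effect only |
|---|---|---|---|---|---|
| 0.6 | 32% | 0.327 | 33% | <0.1% | 2.5% |
| 0.7 | 42% | 0.283 | 42% | <0.1% | 2.5% |
| 0.8 | 60% | 0.231 | 57% | <0.1% | 2.5% |

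The equality across situations follows from an F test having no sign and from three equal arms being symmetric. It shows what the rule cannot distinguish, not how likely a misreading is.

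**2. Which arm is the experiment group.** Suppose PRIIS added to CCT gives 0.5 SD and CCT alone gives nothing. The reported CCT effect is then:
- 0 if the experiment group is CCT+PRIIS control;
- (0.5+0)/2 = 0.25 SD if both CCT arms are pooled;
- 0.5 SD if it is CCT+PRIIS.

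**3. Immediate change, if left unsubtracted.** With no treatment effect and an assumed shared practice gain of 0.3 SD, a within-arm change (SE √(2(1−r)/15) = 0.231, 0.200, 0.163) is a significant gain in 25%, 32% and 44% of trials. After subtraction, the rate in favour of the active arm is 2.5% whatever the shared practice.

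**4. Durability.** Take a true 0.25 SD loss after endpoint in the active arm, and practice at the third exposure shared by all arms. The table gives the chance of a significant decline.

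| r | Within arm, practice 0 | Practice 0.1 SD | Practice 0.2 SD | Between-arm difference, any shared practice |
|---|---|---|---|---|
| 0.6 | 19% | 9% | 4% | 11% |
| 0.7 | 23% | 11% | 4% | 14% |
| 0.8 | 33% | 15% | 5% | 19% |

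**5. Cost of replacing one test by several intervals.** Take the CCT and add-on differences, each from baseline to endpoint and from baseline to follow-up: four 95% CIs. In simulation with no effects, at least one excludes zero in about 16% of trials (about 9% in the favourable direction), against 5% for the interaction. Adding the two endpoint-to-follow-up intervals gives about 21%. The remedy therefore needs one named primary contrast or a multiplicity adjustment.

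**The case against.** The strongest reply is that an omnibus interaction followed by contrasts is a common sequence. The contrasts carry a sign, and no competent analyst holding the arm means would report CCT doing worse as efficacy. That is largely fair: the more credible risk is crediting an add-on difference to CCT. But the sentence that defines efficacy does not use the contrasts, and they leave the experiment arm open.

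Pairing an experiment with a control contrast, and then referring to test statistics, makes a subtraction the natural intention for the immediate effect. The control is also clear, since only one arm receives CCT control. I accept both points; what remains is that the subtraction is unwritten and the experiment arm is unnamed.

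For durability, the control arm's change is estimated, because contrasts are made in every group. The harm arises only if the arms are read separately, and the practice gains above are assumptions.

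Aims 2 and 3, which this analysis serves, are not in the text available. They may state a direction or a comparison, although the efficacy sentence refers to none.

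The word trends could mean linear time. The figures would then change, but the lack of sign and of a named pair would not.

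**Conclusion.** The point holds as a defect in the decision rule and in the wording of the contrasts in section 5.0, and it should be fixed. Followed literally, the rule gives the same conclusion for benefit, for harm and for an add-on effect alone: 32%, 42% and 60% of trials for a 0.5 SD effect under the stated assumptions. The percentages are illustrative; the finding rests on the text.

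A reader might infer more, and the documents do not support it:
- *That the plan has no randomised comparison, or that practice biases the interaction.* The interaction compares arms, and practice shared by all arms cancels in it.
- *That the immediate effect will be judged without the control arm.* A control contrast is planned, and a subtraction is probably intended.
- *That the trial has no directional or pairwise hypothesis.* The unseen Aims prevent that conclusion.

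For a pilot of 45 the consequence is limited. The planned model already yields every arm-by-visit mean, so the needed differences can be obtained from it. What is missing is a prior commitment to which one counts.

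**What to change.** Keep the mixed model, treat time as categorical, and make these changes in section 5.0.

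- **Name one primary contrast** on the NIH-EXAMINER composite, chosen by the sponsor according to its Aims. An example is CCT = (CCT+PRIIS control) minus (CCT control+PRIIS control), as the difference in change from baseline to endpoint. Test it two-sided at 5%.
- **Replace the efficacy sentence** with, for example: *Efficacy on EF will be concluded only if the primary between-arm difference in change is significant and favours the active arm; the omnibus interaction and within-arm changes are descriptive.*
- **Report the other between-arm differences with 95% CIs** as secondary estimates without efficacy claims, or with a stated multiplicity adjustment. These are PRIIS added to CCT = (CCT+PRIIS) minus (CCT+PRIIS control), the baseline-to-follow-up differences, and the endpoint-to-follow-up differences.
- **State that the PRIIS contrast is an add-on effect**, since no arm receives PRIIS without CCT. It may act partly through completion of CCT. Under Phase 4, "a common goal for all participants in each group will be completing weekly CCT/CCT active control assignments", and PRIIS controls rehearse the same task, so on that goal only the strategy technique differs.

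**Cost.** SAP wording and a few ESTIMATE statements in the planned Proc Mixed; no new data. The price is visible imprecision. The CI half-width is 1.989 × SE = 0.65, 0.56, 0.46 SD for r = 0.6, 0.7, 0.8, and 80% power needs a true difference of 0.93, 0.80, 0.66 SD. A 0.25 SD between-arm loss after endpoint is detected in only 11–19% of trials, fewer than the within-arm contrast detects (19–33%) if there is no practice effect. The change removes shared practice from the comparison; it does not make durability demonstrable at this size.

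Separately, Phase 4 and Phase 6 of section 1.0 differ on who attends the one-month follow-up. That is its own point, and those passages must be reconciled.

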1.0 Study Design and Methods

Study Design

To address the study objectives, a pilot randomized controlled trial will be conducted.

Study population:

Group 1: Veterans

A convenience sample of Veterans , who are screened and diagnosed with Parkinson's disease (PD) and mild cognitive impairment in the executive function domain will be enrolled. Targeted enrollment for the intervention is 45; they will be randomized to one of three groups: CCT+PRIIS (n=15), CCT+PRIIS control (n=15) or CCT control +PRIIS control (n=15).

Group 2: Knowledgeable Informants

We will also enroll knowledgeable informants/caregivers of the enrolled Veterans. Thus, we will be enrolling civilians (however it is possible that caregiver could be a Veteran and this is acceptable). The purpose for enrolling a caregiver is to obtain their perspective on functional changes related to cognitive impairment in the Veteran living with PD. To obtain their perspective, they will complete the PD-Cognitive Functional Rating Scale (PD-CFRS) at three different time points during the study. The planned activities for the caregiver are the following: consent, demographic form, PD-CFRS at three different time points. The consent form, demographic form and PD-CFRS will be completed at their first visit. We will mail them the form when their Veteran completes the RCT, we will mail them the form again one month later. A knowledgeable informant/caregiver is not required in order for the Veterans to enroll. Targeted enrollment is 45, however we anticipate having to enroll 60 civilians due to Veterans being withdrawn – and thus the associated civilian will need to be withdrawn.

Below we list the inclusion and exclusion criteria for both Veterans and Knowledgeable Informants.

Group 1: Veterans

In general, eligibility criteria target Veterans with idiopathic PD and not other forms of parkinsonism. Thus, only Veterans older than 50 with PD diagnosed according to UK Parkinson's Disease Society Brain Bank

Diagnostic Criteria will be eligible. PD medication can influence cognitive function, thus, only participants receiving stable medication (i.e., no changes in medication or dose for the past month) and who are expected to remain on stable medication for the duration of the RCT will be eligible.

Inclusion criteria for Veterans:

- Diagnosis of PD as determined by the UK Parkinson's Disease Society Brain Bank Diagnostic Criteria⁴⁶
- age 50 and older

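### The planned sustainability contrast, endpoint versus follow-up within each group, cannot show that a CCT benefit over control persists

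*Combined protocol and SAP*

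**What the plan says.** The design has three arms: "CCT+PRIIS (n=15), CCT+PRIIS control (n=15) or CCT control +PRIIS control (n=15"). Under Phase 3: Baseline data collection, "Repeated measures/study outcomes are included in a standardized battery of test that will be repeated at baseline, endpoint and follow-up". Phase 6 places follow-up one month after the last intervention session.

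Section 5.0 Data Analysis fits a mixed model with random subject effects: "Parameters will be estimated using measurements from baseline, endpoint, and follow-up". Three analyses come from it:

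- **Overall test:** "The group by time interaction parameter will be used to examine the difference of the trends between the three groups". The plan links its significance to efficacy on executive function over time.
- **Immediate effect:** "an experiment group contrast will be formed using test score means at baseline and endpoint and a control group contrast will be made" from the same pair of visits.
- **Sustainability:** "To assess sustainability of CCT effects, contrasts using means of test scores at endpoint and follow-up will be made for each group".

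On test statistics for the contrasts, it says "Estimates of variance components from mixed-model analysis will be used to calculate test statistics". For sustainability the section gives no margin, no contrast from baseline to follow-up, no comparison between arms, no significance level and no rule for interpreting the result. A level of 0.05 appears only for the ANCOVA comparability checks, where the "type I error rate ($\alpha=0.05$) will be adjusted for multiple comparisons using Bonferroni corrections".

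**The concern.** A contrast of endpoint with follow-up tests whether scores changed after training stopped. A significant decline would count against sustainability. The only result compatible with sustainability is a non-significant one, and small arms and noisy scores make that result more likely. Without a margin, failing to find a decline does not show that the effect was kept.

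The contrast also omits the quantity of interest, which is whether Veterans given CCT are still better off than controls at follow-up, compared with where they started. Within one arm, the change from endpoint to follow-up mixes loss of training effect, retest gain on a battery given again a month later, and disease course.

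Section 3.0 says these pilot data will support a larger grant proposal. A durability statement resting on this contrast could be carried into the design of the next trial.

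**Working it through.** The plan states no power, effect size, SD, correlation or margin, so there is no figure of its own to reproduce.

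**Inputs from the plan.** n = 15 per arm; three visits; variance components from the mixed model. With 45 participants, three arms and three visits, residual df = (45 − 3) × (3 − 1) = 84, before covariates and dropout.

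**Assumed inputs.** Two-sided 0.05; correlation ρ between visits 0.6 to 0.8; an endpoint effect d of 0.3 to 0.5 SD, completely lost by follow-up; no dropout.

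**Step 1: CCT never worked.** If there is also no retest gain or disease drift between the two visits, the expected change is zero. The contrast is then non-significant in 1 − 0.05 = 95% of trials, per arm and outcome. This needs no assumption about SD or correlation.

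**Step 2: an effect existed and was wholly lost.** In SD units the within-arm SE = √(2(1 − ρ)/n). At ρ = 0.7 this is √(0.6/15) = 0.20. A loss of 0.4 gives noncentrality 0.4/0.20 = 2.0 and, from the noncentral t with 84 df, power 0.51, so the loss is missed 49% of the time. Over the grid, the chance of no significant change is:

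| ρ | loss 0.3 SD | loss 0.4 SD | loss 0.5 SD |
|---|---|---|---|
| 0.6 | 75% | 60% | 43% |
| 0.7 | 68% | 49% | 30% |
| 0.8 | 56% | 32% | 14% |

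Five of the nine cells are below 50%. At a loss of 0.8 SD the miss rate is 2% at ρ = 0.7 and under 1% at ρ = 0.8. A simple paired t with 14 df gives 54% in the central cell instead of 49%.

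**Step 3: retest gain.** If an assumed 0.2 SD retest gain offsets part of a 0.5 SD loss, the net change is 0.3 SD. The miss rates at ρ = 0.7 and 0.8 rise from 30% and 14% to 68% and 56%.

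**Step 4: requiring a significant gain first.** The gain and the loss have the same SE. They share the endpoint visit, so their estimates correlate at 0.5. In simulated normal draws, given a significant within-arm gain, the loss is missed 33% of the time in the central cell and about 10% to 52% over the grid. The joint probability of a significant gain followed by a missed total loss is about 9% to 17%.

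**Step 5: the direct contrast.** For the difference between two arms of 15 in change from baseline to follow-up, SE = √(4(1 − ρ)/15). At ρ = 0.7 this is √0.08 = 0.283, and the 95% half-width is 1.989 × 0.283 = 0.56 SD. At ρ = 0.5 and 0.8 it is 0.73 and 0.46 SD. If the effect is wholly lost, the CI excludes zero in favour of CCT in about 2.5% of trials. If a 0.4 SD effect is fully retained, it does so in about 29% at ρ = 0.7, and in 15% to 57% over the grid of effects and correlations in Step 2.

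**The case against.** The strongest reply has four parts.

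**No reading rule is written.** A reader might infer that a wholly lost effect will usually be declared sustained. The documents do not support that. They never say a non-significant change will be called sustained; that is the natural reading of the contrast, but it is an inference. Nor do they give the effect size, SD or correlation on which "usually" would depend. With the pooled df that the plan's wording implies, the miss rate is below one half in most cells of the grid. Higher miss rates apply to a between-arm version of the contrast, which the plan does not specify for sustainability.

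**An immediate effect is assessed first.** Speaking of sustained effects presupposes one, and Step 4 shows that requiring it lowers the miss rate. That stands. However, the plan does not make the sustainability contrast conditional on a significant gain.

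**The control arm is followed too.** Contrasts are made for each group, so a shared retest gain would be visible in the double-control arm. This helps informally, but no subtraction is planned. Subtracting would remove shared retest gain and still leave a null of no change.

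**Follow-up is in the model.** The group-by-time test covers all three visits. It can be significant from an endpoint effect alone, and the plan ties it to efficacy. The baseline-to-follow-up difference is estimable from the planned model, which makes the remedy cheap; it is not yet a planned analysis.

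**Conclusion.** The point holds as a gap in the analysis. Followed as written, the sustainability contrast cannot establish that a CCT benefit over control persists, because its null is no change, it has no margin, and it makes no comparison with control at follow-up. This part does not depend on any assumed effect size.

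The size of the risk does depend on assumptions. With 15 per arm and about 84 df, a total loss of 0.3 to 0.5 SD is missed within an arm about 14% to 75% of the time for correlations of 0.6 to 0.8. The figure is lower if a significant endpoint gain is required, and higher with retest gain or dropout. The matter should be corrected before analysis. In a pilot it bears on how durability is reported, not on whether the trial can run.

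**What to change.** In section 5.0 Data Analysis:

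1. Define the sustained effect as the CCT-minus-control difference in change from baseline to follow-up, from the mixed model already planned, reported with a 95% CI. Name the arms compared. CCT with PRIIS control against the double control isolates CCT; CCT+PRIIS against the double control measures the combination.
2. Describe an effect as sustained only if that CI excludes zero in favour of CCT. Otherwise report it as an estimate with its interval. A favourable point estimate must not suffice, since under no effect it occurs half the time.
3. Keep the endpoint-to-follow-up change in each group as descriptive, with its CI, and state that its non-significance is not evidence of sustainability.

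The cost is one added contrast for each CCT arm and a few sentences; no new data are needed. The downside is precision. With a half-width of about 0.46 to 0.73 SD (correlation 0.8 to 0.5), a moderate effect that truly persists will often not be confirmed in this pilot, and the report should say so.

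### Depression, anxiety and apathy are both fixed covariates and secondary outcomes; if all three scales are modelled as planned, each is adjusted for itself

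*Combined protocol and SAP*

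**What the plan says.** Section 5.0 Data Analysis describes one model for Aims 2 and 3: "data will be analyzed using a two-level longitudinal mixed effects model with random subject effects". On adjustment it says "Covariates will include medication dose, anxiety, apathy, and depression level", without saying whether these are baseline values or values at each visit. On the response it says "Parameters will be estimated using measurements from baseline, endpoint, and follow-up", so the baseline score is itself a response row. The test of interest is stated as "The group by time interaction parameter will be used to examine the difference of the trends between the three groups". The scope is then given: "This modeling process will be reported for each outcome of interest in Aims 2 and 3".

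In section 1.0, Phase 3, Table 3 is introduced with "Repeated measures/study outcomes are included in a standardized battery of test that will be repeated at baseline, endpoint and follow-up". It includes the rows "Beck Depression Inventory-II 2° Depression 10" and "Beck Anxiety Inventory 2° Anxiety 10", and the Starkstein Apathy Scale is marked as a secondary outcome in the same way. The text above Table 3 says that tests given at screening, naming the BDI-II and the Beck Anxiety Inventory among its examples, are not repeated at baseline. The screening score therefore serves as their baseline score.

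No sentence removes a scale from the covariates when that scale is the outcome.

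**The concern.** The three scales in Table 3 are the only depression, anxiety and apathy measures in the plan, so the covariates and the outcomes are the same variables. Applied literally, the depression model has depression on both sides, and likewise for anxiety and apathy. That touches 3 of the 17 outcomes in Table 3 (1 composite + 3 domain scores + 13 others).

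At stake is whether the plan can report a valid training effect on mood and apathy. The damage depends on the time point of the covariates, which the plan leaves open. One choice makes the model useless for these outcomes. The other lets it run and print plausible output in which some standard errors are wrong.

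**Working it through.** The plan states no effect size, SD or power, so there is no figure to reproduce. Inputs from the documents: 15 Veterans per arm, three arms, three visits, random subject effects, group-by-time test, alpha 0.05. Assumptions: total variance 1 at each visit, within-subject correlation ρ (so subject variance ρ and residual variance 1−ρ), and no true effect.

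**Visit values as covariates.** The outcome is regressed on itself. In a fit to simulated data with a real effect built in, the own-score coefficient was 1, every group, time and interaction term was 0, and the residual sum of squares was about 1e-28.

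**Baseline values as covariates, complete data, ρ = 0.7.**

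- The covariate is constant within a subject, so its coefficient comes from the subject means: b = (1+2ρ)/3 = 2.4/3 = 0.8.
- The variance of a subject mean after adjustment is 0.8 × (1−0.8) = 0.16. Subtracting residual variance/3 = 0.30/3 = 0.10 leaves an estimated subject variance of 0.06, against 0.70 without the covariate. A 400-trial simulation gave 0.06 and 0.71.
- Model SE of an arm difference at endpoint: sqrt(2 × (0.06+0.30)/15) = 0.219.
- True SD of that difference: the variance of (endpoint − 0.8 × baseline) is 1 + 0.64 − 2 × 0.8 × 0.7 = 0.52, so sqrt(2 × 0.52/15) = 0.263. The ratio is 0.219/0.263 = 0.83, about 17% too small. A 40,000-trial simulation gave 0.220 and 0.264.
- Change contrast: the covariate cancels from endpoint − baseline. The SE is sqrt(4 × 0.30/15) = 0.283 with or without it. On one simulated dataset the four interaction estimates and their SEs were identical both ways (for example 1.0595, SE 0.3273).

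**Simulation over a range of ρ** (REML random intercept, 1,000 trials per setting, Monte Carlo error about 0.7 percentage points at 0.05). The endpoint columns are for complete data with the own baseline as covariate. The last two columns give the interaction type I error with the own baseline, and without it in brackets.

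| ρ | Endpoint model SE | Empirical SD | Shortfall | Endpoint rejection | Interaction, complete | Interaction, 25% dropout |
|---|---|---|---|---|---|---|
| 0.1 | 0.334 | 0.365 | 8% | 0.067 | 0.062 (0.048) | 0.083 (0.044) |
| 0.3 | 0.310 | 0.369 | 16% | 0.096 | 0.052 (0.056) | 0.077 (0.054) |
| 0.5 | 0.272 | 0.329 | 17% | 0.094 | 0.052 (0.051) | 0.077 (0.057) |
| 0.7 | 0.220 | 0.252 | 13% | 0.081 | 0.042 (0.056) | 0.070 (0.054) |
| 0.85 | 0.160 | 0.194 | 18% | 0.113 | 0.053 (0.047) | 0.080 (0.051) |

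Dropout matters because, once visits are missing, the interaction no longer rests on within-subject differences alone. It then draws on the estimated subject variance, which is wrong. The adjusted variance is also no longer equal across visits: at ρ = 0.7 it is 0.2² × 1 = 0.04 at baseline and 0.52 at endpoint, while the model assumes 0.36 at both.

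The 25% is 1 − 45/60, from the informant enrolment figures in section 1.0. In the simulation, 25% of subjects missed follow-up and about half of those also missed endpoint, with no imputation.

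**The case against.** The strongest reply is about scope. The modelling sentence covers Aims 2 and 3, whose text is not in the supplied document. Section 3.0 describes the Aims in terms of cognition and daily activities, and section 5.0 interprets significance in terms of executive function. If mood lies outside those Aims, no self-adjustment is planned. This stands, and it is why the point is conditional. A reader might infer that every outcome is affected; the text does not support that. If mood is outside the Aims, however, three listed secondary outcomes have no stated model, so wording is still needed.

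A reader might also infer that the plan fails however the covariates are defined. It does not. The comparisons named in section 5.0 are the interaction and contrasts between visits, and with complete data a baseline covariate cancels from them. The standard-error shortfall belongs to an arm difference at a single visit, which the plan does not name as a test. What remains on the baseline reading is the inflation under dropout, and any single-visit comparison reported from the same model.

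The 25% dropout is open to challenge. The plan also uses withdrawal for people who fail screening, so loss after randomization may be smaller, and section 5.0 promises imputation without naming a method. Some loss is nevertheless built in: under Phase 4, participants who stop the program early are scheduled for the one-month visit only if they completed at least 12 hours.

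Finally, a degenerate fit would be conspicuous in the output and is unlikely to be reported as a finding of no effect. That is fair for visit values. It does not help with baseline values, where the model runs normally. The planned multicollinearity check would not reveal the problem either, because it compares predictors with one another and not with the response.

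**Conclusion.** The overlap is real and the plan contains no exception for it. Provided the three scales are modelled under section 5.0, the consequence depends on the covariate time point:

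- **Visit values:** no treatment effect can be estimated for these outcomes.
- **Baseline values, complete data:** the planned group-by-time test is essentially unaffected, with type I error 0.042 to 0.053 for correlations of 0.3 or more. The endpoint arm-difference SE is about 8 to 18% too small.
- **Baseline values, assumed 25% dropout:** the interaction type I error is 0.070 to 0.083, against 0.044 to 0.057 without the own-baseline covariate.

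The within-subject correlation (0.1 to 0.85) and the dropout rate are assumptions. The primary NIH-EXAMINER composite is not self-adjusted, so this is a correction to secondary analyses and does not challenge the main result.

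**What to change.** Add to section 5.0: when the BDI-II, Beck Anxiety Inventory or Starkstein Apathy Scale is the outcome, that scale is omitted from the covariates and its baseline score enters only as the baseline response; in all models the depression, anxiety and apathy covariates are baseline values. The defect does not require dropping the other two mood scales from each of these models. It would also help to list which Table 3 outcomes belong to Aims 2 and 3.

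With the own covariate removed, the simulated interaction type I error was 0.047 to 0.056 with complete data and 0.044 to 0.057 with 25% dropout, and model standard errors agreed with empirical SDs within about 4%. The cost is a sentence or two of analysis wording, with no change to data, visits or participants.
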